6.2 Correlative Research

A mandatory correlative research component is part of this study, the patient will be automatically registered onto this component (see Sections 3.19g and 14.0).

An optional correlative research component is part of this study, there will be an option to select if the patient is to be registered onto this component (see Section 17.0).

- Patient has/has not given permission to have additional tissues collected from their diagnostics biopsy submitted for research.
- Patient has/has not given permission to obtain the optional fresh research tissue biopsy prior to starting treatment. **(Mayo patients only)**

6.3 Documentation of IRB approval must be on file in the Registration Office before an investigator may register any patients.

In addition to submitting initial IRB approval documents, ongoing IRB approval documentation must be on file (no less than annually) at the Registration Office [REDACTED]. If the necessary documentation is not submitted in advance of attempting patient registration, the registration will not be accepted and the patient may not be enrolled in the protocol until the situation is resolved.

When the study has been permanently closed to patient enrollment, submission of annual IRB approvals to the Registration Office is no longer necessary.

- 6.4 Prior to accepting the registration, registration application will verify the following:
 - IRB approval at the registering institution
 - Patient eligibility
 - Existence of a signed consent form
 - Existence of a signed authorization for use and disclosure of protected health information
- 6.5 At the time of registration, the following will be recorded:
 - Patient has/not given permission to store and use his/her sample(s) for future research of lymphoma by the Lymphoma SPORE.
 - Patient has/not given permission to store and use his/her sample(s) for future research to learn, prevent, or treat other health problems.
 - Patient has/not given permission for Lymphoma SPORE to give his/her sample(s) to researchers at other institutions.
- 6.6 Treatment cannot begin prior to registration and must begin \leq 21 days after registration.
- 6.7 Pretreatment tests/procedures (see Section 4.0) must be completed within the guidelines specified on the test schedule.
- 6.8 All required baseline symptoms (see Section 10.6) must be documented and graded.
- 6.9a Treatment on this protocol must commence at the University of Iowa Holden Comprehensive Cancer Center or the Mayo Clinic Cancer Center under the supervision of a physician investigator registered with NCI Pharmaceutical Management Branch (PMB) and the Lymphoma SPORE Operations Office.
- 6.9b Blood draw kit is available on site.
- 6.9c Patient questionnaire booklet is available on site.

7.0 Protocol Treatment

7.1 Treatment Schedule – Arm A: Rituximab

Agent	Dose	Route	Day	Cycle Length
Rituximab ¹	375 mg/m ² /day	IV	1, 8, 15, 22	3 months

1. Substitution of a rituximab biosimilar covered by patients' insurance plan is acceptable for Arm A.

The following pre-medications are suggested prior to rituximab: acetaminophen 650-1000 mg PO 30 minutes prior to rituximab and every 4 hours as needed for infusion related reactions, diphenhydramine 50 mg PO 30 minutes prior to rituximab, diphenhydramine 25 mg IV every 4 hours as needed for infusion related reactions, meperidine 25 mg IV push as needed for rigors, may repeat x 1 dose if first dose is ineffective

7.2 Treatment Schedule – Arm B: Zevalin

Agent	Dose	Route	Day	Cycle Length
Rituximab ¹	250 mg/m ² /day	IV	1, 8	3 months
Zevalin	0.3 mCi/kg or 0.4 mCi/kg**	IV	8*	

- * Administer within 4 hours of completion of rituximab infusion.
- ** Maximum dose = 32 mCi. Dose at 0.4 mCi/kg for patients with platelet counts greater than or equal to 150,000/mm³ and at 0.3 mCi/kg for patients with platelet counts 100,000 to 149,000/mm³
- 1. Substitution of a rituximab biosimilar covered by patients' insurance plan is not allowed for Arm B.

The following pre-medications are suggested prior to rituximab: acetaminophen 650-1000 mg PO 30 minutes prior to rituximab and every 4 hours as needed for infusion related reactions (maximum of 4000 mg in 24 hours), diphenhydramine 50 mg PO 30 minutes prior to rituximab, diphenhydramine 25 mg IV every 4 hours as needed for infusion related reactions, meperidine 25 mg IV push as needed for rigors, may repeat x 1 dose if first dose is ineffective.

- 7.3 For this protocol, patients randomized to Zevalin can be treated either at the enrolling site or referred to Mayo Clinic Rochester, Arizona, or Florida for the Day 1, 8 rituximab and Zevalin on Day 8. The enrolling site is also permitted to provide Day 1 rituximab if this is prearranged and coordinated with the Zevalin site. This can be arranged by calling the study [REDACTED] after the patient has been registered.

8.0 Dosage Modification Based on Adverse Events

- 8.1 There are no dose modifications in this study.

9.0 Ancillary Treatment/Supportive Care

- 9.1 Antiemetics may be used at the discretion of the attending physician.
- 9.2 Patients may receive allopurinol at the discretion of the treating physician.
- 9.3 It is very unlikely that the patient would require blood products or growth factors. However, the patient may be administered hematopoietic growth factors (erythropoietin, GM-CSF, G-CSF, pegfilgrastim, oprelvekin) at the discretion of the treating physician. These should not be used prophylactically. The use of these agents should be recorded.
- 9.4 Rituximab reactions: Patients who experience rituximab reactions may receive oral or IV corticosteroids in order to enable completion of rituximab therapy. Suggested doses are 100 mg of hydrocortisone IV or 50-100 mg methylprednisolone (Solu-Medrol) IV pre-rituximab or to treat a rituximab reaction that does not respond to diphenhydramine and acetaminophen. Patients who experience a reaction that requires IV steroids may be pretreated with corticosteroids at the next dose.
- 9.5 Patients found to have immunoglobulin deficiency on pre-treatment testing may receive IVIG at physician discretion and per recommended guidelines.

10.0 Adverse Event (AE) Reporting and Monitoring

10.1 Adverse Event Characteristics

CTCAE term (AE description) and grade: The descriptions and grading scales found in the revised NCI Common Terminology Criteria for Adverse Events (CTCAE) version 4.0 will be utilized for AE reporting. All appropriate treatment areas should have access to a copy of the CTCAE version 4.0. A copy of the CTCAE version 4.0 can be downloaded from the CTEP web site:

(http://ctep.cancer.gov/protocolDevelopment/electronic_applications/ctc.htm)

10.11 Adverse event monitoring and reporting is a routine part of every clinical trial. First, identify and grade the severity of the event using the CTCAE version 4.0. Next, determine whether the event is expected or unexpected (see Section 10.2) and if the adverse event is related to the medical treatment or procedure (see Section 10.3). With this information, determine whether the event must be reported as an expedited report (see Section 10.4). **Important:** Expedited adverse event reporting requires submission of a MedWatch report(s). Expedited reports are to be completed within the timeframes and via the mechanisms specified in Sections 10.4. All AEs reported via expedited mechanisms must also be reported via the routine data reporting mechanisms defined by the protocol (see Sections 10.52 and 18.0).

10.12 Each CTCAE term in the current version is a unique representation of a specific event used for medical documentation and scientific analysis and is a single MedDRA Lowest Level Term (LLT). Grade is an essential element of the Guidelines and, in general, relates to **severity** for the purposes of regulatory reporting to NCI.

NOTE: A severe AE, as defined by the above grading scale, is **NOT** the same as serious AE which is defined in the table in Section 10.4.

10.2 Expected vs. Unexpected

- The determination of whether an AE is expected is based on the agent-specific information provided in Section 15.0 of this protocol.
- Unexpected AEs are those not listed in the agent-specific information provided in Section 15.0 of this protocol.

NOTE: “Unexpected adverse experiences” means any adverse experience that is neither identified in nature, severity, or frequency of risk in the information provided for IRB review nor mentioned in the consent form.

10.3 Assessment of Attribution

When assessing whether an adverse event is related to a medical treatment or procedure, the following attribution categories are utilized:

- Definite - The adverse event *is clearly related* to the agent(s).
- Probable - The adverse event *is likely related* to the agent(s).
- Possible - The adverse event *may be related* to the agent(s).
- Unlikely - The adverse event *is doubtfully related* to the agent(s).
- Unrelated - The adverse event *is clearly NOT related* to the agent(s).

Events determined to be possibly, probably or definitely attributed to a medical treatment suggest there is evidence to indicate a causal relationship between the drug and the adverse event.

10.4 Expedited Reporting Requirements for CIP Studies using Commercial Agent(s) ONLY:

Expedited Reporting Requirements for Adverse Events that Occur in a Non-IND/IDE trial within 30 Days of the Last Administration of a Commercial Agent^{1,2}

FDA REPORTING REQUIREMENTS FOR SERIOUS ADVERSE EVENTS (21 CFR Part 312)

NOTE: Investigators **MUST** immediately report to the sponsor **ANY** Serious Adverse Events, whether or not they are considered related to the investigational agent(s)/intervention (21 CFR 312.64)

An adverse event is considered serious if it results in **ANY** of the following outcomes:

- 1) Death
- 2) A life-threatening adverse event
- 3) An adverse event that results in inpatient hospitalization or prolongation of existing hospitalization for \geq 24 hours
- 4) A persistent or significant incapacity or substantial disruption of the ability to conduct normal life functions
- 5) A congenital anomaly/birth defect.
- 6) Important Medical Events (IME) that may not result in death, be life threatening, or require hospitalization may be considered serious when, based upon medical judgment, they may jeopardize the patient or subject and may require medical or surgical intervention to prevent one of the outcomes listed in this definition. (FDA, 21 CFR 312.32; ICH E2A and ICH E6).

ALL SERIOUS adverse events that meet the above criteria **MUST** be immediately reported to the sponsor within the timeframes detailed in the table below.

Hospitalization	Grade 1 Timeframes	Grade 2 Timeframes	Grade 3 Timeframes	Grade 4 & 5 Timeframes
Resulting in Hospitalization \geq 24 hrs		7 Calendar Days		24-Hour 3 Calendar Days
Not resulting in Hospitalization \geq 24 hrs	Not required		7 Calendar Days	

NOTE: Protocol specific exceptions to expedited reporting of serious adverse events are found in section 10.41 of the protocol.

Expedited AE reporting timelines are defined as:

- “24-Hour; 3 Calendar Days” - The AE must initially be reported via MedWatch within 24 hours of learning of the AE, followed by a complete expedited report within 3 calendar days of the initial 24-hour report.
- “7 Calendar Days” - A complete expedited report on the AE must be submitted within 7 calendar days of learning of the AE.

¹Serious adverse events that occur more than 30 days after the last administration of investigational agent/intervention and have an attribution of possible, probable, or definite require reporting as follows:

Expedited 24-hour notification followed by complete report within 3 calendar days for:

- All Grade 4, and Grade 5 AEs

Expedited 7 calendar day reports for:

- Grade 2 adverse events resulting in hospitalization or prolongation of hospitalization
- Grade 3 adverse events

² For studies using PET or SPECT IND agents, the AE reporting period is limited to 10 radioactive half-lives, rounded UP to the nearest whole day, after the agent/intervention was last administered. Footnote “1” above applies after this reporting period.

Effective Date: May 5, 2011

Additional Instructions:

1. An increased incidence of an expected adverse event (AE) is based on the patients treated for this study at their site. A list of known/expected AEs is reported in the package insert or the literature, including AEs resulting from a drug overdose.
2. Submit form to the FDA, [REDACTED]
[REDACTED]
[REDACTED]
[REDACTED]

Reporting Serious Adverse Events to Acrotech Biopharma: The Investigator must notify Acrotech Biopharma of any event that meets one of the criteria for an SAE within 24 hours of first knowledge. For the initial report, please complete a standard MedWatch form and email to [REDACTED] with all relevant documentation (laboratory tests, hospital admission/discharge summary, etc.). Please assure that patient identifiers are redacted from all documentation, except for patient initials and date of birth.

Acrotech Biopharma:

SAE Email: [REDACTED]

10.41 Special Situations for Expedited Reporting

EXPECTED Serious Adverse Events

An expedited report may not be required for specific Grade 1, 2, 3 and 4 Serious Adverse Events where the AE is **EXPECTED**. Any protocol specific reporting procedures MUST BE SPECIFIED BELOW and will supercede the standard Expedited Adverse Event Reporting Requirements. Note: These adverse events must still be reported through the routine reporting mechanism [i.e. Nadir/Adverse Events Form]; see footnote 1.

System Organ Class (SOC)	Adverse event/ Symptoms	CTCAE Grade at which the event will not be expeditedly reported. ¹
Blood and lymphatic system disorders	Anemia	≤ Grade 4
Investigations	White blood cell decreased	≤ Grade 4
	Lymphocyte count decreased	≤ Grade 4
	Neutrophil count decreased	≤ Grade 4
	Platelet count decreased	≤ Grade 4

¹ These exceptions only apply if the adverse event does not result in hospitalization. If the adverse event results in hospitalization, then the standard expedited adverse events reporting requirements must be followed.

Specific protocol exceptions to expedited reporting should be reported expeditiously by investigators **ONLY** if they exceed the expected grade of the event.

10.5 Other Required Reporting

10.51 **Persistent or Significant Disabilities/Incapacities**

Any AE that results in persistent or significant incapacity or substantial disruption of the ability to conduct normal life functions (formerly referred to as disabilities), congenital abnormalities or birth defects, must be reported immediately if they occur at any time following treatment with an agent under an IND/IDE since they are considered to be a serious AE and must be reported to the sponsor as specified in 21 CFR 312.64(b).

10.52 **Death**

Any death occurring within 30 days of the last dose, regardless of attribution to an agent/intervention under an IND/IDE requires expedited reporting within 24-hours.

Any death occurring greater than 30 days with an attribution of possible, probable, or definite to an agent/intervention under an IND/IDE requires expedited reporting within 24-hours.

Reportable categories of Death

- Death attributable to a CTCAE term.
- Death Neonatal: A disorder characterized by cessation of life during the first 28 days of life.
- Death NOS: A cessation of life that cannot be attributed to a CTCAE term associated with Grade 5.
- Sudden death NOS: A sudden (defined as instant or within one hour of the onset of symptoms) or an unobserved cessation of life that cannot be attributed to a CTCAE term associated with Grade 5.
- Death due to progressive disease should be reported as **Grade 5 “Neoplasms benign, malignant and unspecified (incl cysts and polyps) – Other (Progressive Disease)”** under the system organ class (SOC) of the same name. Evidence that the death was a manifestation of underlying disease (e.g., radiological changes suggesting tumor growth or progression; clinical deterioration associated with a disease process) should be submitted.

10.53 Secondary Malignancy

- A **secondary malignancy** is a cancer caused by treatment for a previous malignancy (e.g., treatment with investigational agent/intervention, radiation or chemotherapy). A secondary malignancy is not considered a metastasis of the initial neoplasm.
- All secondary malignancies that occur following treatment with an agent under an IND/IDE be reported. Three options are available to describe the event:
 - Leukemia secondary to oncology chemotherapy (e.g., Acute Myelocytic Leukemia [AML])
 - Myelodysplastic syndrome (MDS)
 - Treatment-related secondary malignancy
- Any malignancy possibly related to cancer treatment (including AML/MDS) should also be reported via the routine reporting mechanisms outlined in each protocol.

10.54 Second Malignancy

- A second malignancy is one unrelated to the treatment of a prior malignancy

(and is NOT a metastasis from the initial malignancy). Second malignancies require ONLY routine reporting.

10.6 Required Routine Reporting

Adverse events to be graded at each evaluation and pretreatment symptoms/conditions to be evaluated at baseline per the CTCAE v4.0 grading unless otherwise stated in the table below:

System Organ Class (SOC)	Adverse event/Symptoms	Baseline	Each evaluation
Investigations	Neutrophil count decreased	X	X
	Platelet count decreased	X	X
	White blood cell decreased	X	X
Skin and subcutaneous tissue disorders	Rash maculo-papular	X	X

10.61 Submit via appropriate MCCC Case Report Forms (i.e., paper or electronic, as applicable) the following AEs experienced by a patient and not specified in Section 10.6

10.611 Grade 2 AEs deemed *possibly, probably, or definitely* related to the study treatment or procedure.

10.612 Grade 3 and 4 AEs regardless of attribution to the study treatment or procedure.

10.613 Grade 5 AEs (Deaths)

10.6131 Any death within 30 days of the patient's last study treatment or procedure regardless of attribution to the study treatment or procedure.

10.6132 Any death more than 30 days after the patient's last study treatment or procedure that is felt to be at least possibly treatment related must also be submitted as a Grade 5 AE, with a CTCAE type and attribution assigned.

10.62 Refer to the instructions in the Forms Packet (or electronic data entry screens, as applicable) regarding the submission of late occurring AEs following completion of the Active Monitoring Phase (i.e., compliance with Test Schedule in Section 4.0).

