16.34 Adverse Events: All eligible patients that have initiated treatment will be considered evaluable for assessing adverse event rate(s). The maximum grade for each type of adverse event will be recorded for each patient, and frequency tables

will be reviewed to determine patterns. Additionally, the relationship of the adverse event(s) to the study treatment will be taken into consideration. Rates of individual adverse events (grade 3 and higher) will be compared between arms using a Fisher's exact test.

16.4 Correlative Research: The correlative endpoints listed below will be evaluated in each arm independently and may also be compared between the two arms. For each measure, values may be investigated with respect to response (CR vs. less than CR) using two-sample t-tests (continuous measures) or chi-square tests (categorical measures). Relationship with time to event measures (PFS, TTNT, TTC) will be evaluated using Kaplan-Meier methods and log-rank statistics (categorical measures) or Cox proportional hazards models (continuous measures). For values collected at more than one time point, changes over time will be evaluated using paired-t-tests (continuous measures) or McNemar's or Bhapkar's tests (categorical measures). Endpoints and additional analyses are described below. Analysis involving quality of life are described in Section 16.47.

- 16.41 The incidence of exon 2 bcl2 mutations will evaluated at baseline.
- 16.42 Tissue Tregs and tissue monocytes will be quantified for the on study tumor biopsies. These values will be reported as percentages.
- 16.43 Serum cytokines will be analyzed for each time point (pre-treatment and 6 months). Each cytokine will be evaluated in reference to normal controls and levels will be categorized as normal, elevated, or suppressed.
- 16.44 Vitamin D levels will be evaluated at on study. At each time point, Vitamin D level will be categorized as normal (sufficient) vs. abnormal (insufficient). Vitamin D insufficiency will be defined as a 25 hydroxy-vitamin D (D2 + D3) level <25 ng/mL in the central (Mayo) laboratory.

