For all statistical analyses, p-values <0.05 will be considered statistically significant. For interpreting the clinical significance of effects will be evaluated using the FACT cut-offs described above as well as using Cohen's cut-offs (37): <0.20 =trivial; $0.20-0.50$ =small; $0.50-0.80$ =moderate; and >0.80 =large.

16.5 Data & Safety Monitoring:

- 16.51 The principal investigator(s) and the study statistician will review the study at least twice a year to identify accrual, adverse event, and any endpoint problems that might be developing. The Mayo Clinic Cancer Center (MCCC) Data Safety Monitoring Board (DSMB) is responsible for reviewing accrual and safety data for this trial at least twice a year, based on reports provided by the MCCC Statistical Office.
- 16.52 Adverse Event Stopping Rules (these rules apply to Arm A and Arm B independently): Both Arms A (rituximab) and B (Zevalin) are commercial agents used at the FDA-approved dose with standard CBC and bone marrow criteria. Since the doses are the same, we do not expect any difference in the toxicity profile as described in the label. We note that the Adverse Event Stopping Rule may be adjusted in the event of either (1) the study re-opening to accrual or (2) at any time during the conduct of the trial and in consideration of newly acquired information regarding the adverse event profile of the treatment(s) under investigation. The study team may choose to suspend accrual because of unexpected adverse event profiles that have not crossed the specified rule below.

In our previous study of single-agent rituximab for untreated FL(10), we observed 14% grade 3,4 AEs. In previous Zevalin studies for untreated FL (14) there was, as expected, 15% grade 3 and 17% grade 4 (total 32% grades 3,4) neutropenia that was reversible. There was no grades 3,4 non-hematologic toxicity. These toxicities, if they occur, do so within 12 weeks for both Arms A and B. Accrual will be temporarily suspended to both arms if at any time we observe events considered at least possibly related to study treatment (i.e., an

adverse event with attribute specified as “possible”, “probable”, or “definite”) that satisfy either of the following:

- if 3 or more patients in the first 12 treated patients experience a grade 4 or higher non-hematologic adverse event at least possibly related to treatment.

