- if after the first 12 patients have been treated, 25% of all patients experience a grade 4 or higher non-hematologic adverse event at least possibly related to treatment.

We note that we will review grade 4 and 5 adverse events deemed “unrelated” or “unlikely to be related”, to verify their attribution and to monitor the emergence of a previously unrecognized treatment-related adverse event.

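### Deaths beyond 30 days that the site calls unrelated need not be submitted as Grade 5 AEs, so the attribution review in 16.52 cannot be relied on to see them

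*Combined protocol and SAP*

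**What the plan says.** Section 10.61 sets what sites submit on the routine AE forms.

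- 10.612 asks for "Grade 3 and 4 AEs regardless of attribution to the study treatment or procedure". Section 18, footnote 3, runs the AE form through Cycles 1 and 2, that is months 0 to 6, in both arms.
- 10.6131 takes any death within 30 days of the "last study treatment or procedure regardless of attribution to the study treatment or procedure".
- 10.6132 covers later deaths and says that one "that is felt to be at least possibly treatment related must also be submitted as a Grade 5 AE".

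Expedited reporting splits deaths the same way. Section 10.52 covers "Any death occurring within 30 days of the last dose, regardless of attribution", and after that "Any death occurring greater than 30 days with an attribution of possible, probable, or definite". Footnote 1 of 10.4 applies the same attribution condition to serious events after 30 days.

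Two parts of Section 16 use these data. Section 16.34 states: "Rates of individual adverse events (grade 3 and higher) will be compared between arms using a Fisher's exact test". It gives no time window. Section 16.52 states: "We note that we will review grade 4 and 5 adverse events deemed" unrelated or unlikely to be related, in order to verify attribution and to pick up a treatment-related event not recognized before.

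**The concern.** The most severe grade has the narrowest rule for collection regardless of attribution. After the 30 days, the site's own attribution decides whether a death is submitted as an AE at all. Yet the purpose of the 16.52 review is to check attributions of unrelated or unlikely. A review cannot check a death that nobody was required to submit. No blinding is described, so attribution is made with the treatment known. The accrual-suspension rule in 16.52 counts only events at least possibly related, so this review is the check on the judgment that feeds the rule.

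The 30 days are also tied to the last treatment, and the arms finish dosing two weeks apart. On a clock from Day 1, the window would be shorter in the Zevalin arm.

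**Working it through.** The plan gives no figure on this point to reproduce. The check is a calendar, a tracing of cases, and a rough size.

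**Calendar, if the clock starts at the last dose**

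| | Arm A | Arm B |
|---|---|---|
| Last dose (7.1, 7.2) | Day 22 | Day 8 |
| Plus 30 days | Day 52 | Day 38 |
| Share of months 0 to 6 (183 days) | 52/183 = 28% | 38/183 = 21% |

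The arms differ by 52 − 38 = 14 days. The week 5 to 7 blood counts after Zevalin (Section 4.0) fall at about Day 8 + 35 = 43 to Day 8 + 49 = 57, after the Arm B date.

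**Where a death on Day 60 goes**

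1. *The site considers it at least possibly related.* It is submitted as grade 5 under 10.6132 and reaches 16.34 and the suspension rule.
2. *It is called unrelated, but the fatal event was first a grade 3 or 4 AE.* That AE is submitted under 10.612 and counts in 16.34, which takes grade 3 and higher. What may be lost is the fatal grade, because 16.34 records maximum grade. The 16.52 review sees the event if it was submitted at grade 4.
3. *It is called unrelated, with no preceding grade 3 or 4 AE.* Section 10.61 requires no AE submission. The death goes on the Event Monitoring form (Section 18) and counts as a PFS event (16.31). Section 18 does not say that a CTCAE term or attribution is recorded there, and neither source is named as feeding 16.34 or 16.52.

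**Size**

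The inputs are the 3-year survival figures in Section 1.2 from a cohort given single-course Zevalin: 97% in patients not meeting GELF criteria and 90% overall. Assume a constant hazard, applied to both arms.

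- Hazard per year: h = −ln(S₃)/3, which is 0.0102 at 97% and 0.0351 at 90%.
- Deaths per 58 patients in 183 days: 58 × (1 − exp(−h × 183/365.25)) = 0.29 at 97% and 1.01 at 90%.
- From window close to Day 183, per 58: Arm A 0.21 to 0.72, Arm B 0.23 to 0.80.
- Between Day 38 and Day 52, per 58: 0.02 to 0.08. With 64 per arm: 0.03 to 0.09.

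For one AE term with 64 per arm, Fisher's exact test gives p = 0.058 for 5 against 0 and p = 0.028 for 6 against 0. A shift of less than one expected death per arm is unlikely to move it.

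**The case against.** Four objections have weight.

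*The dates rest on one reading.* Section 10.6131 says treatment or procedure, and procedure is not defined. Research blood at month 6 is mandatory, and a repeat marrow is scheduled then for patients whose first was positive. If these count as study procedures, the window extends past month 6 in both arms and the gap closes. Sections 10.4 (last administration) and 10.52 (last dose) favor the shorter reading but do not settle it.

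*Another route may exist.* The manufacturer-notification rule in 10.4 covers any event meeting a seriousness criterion, with no stated time or attribution limit, and 10.11 requires events reported by expedited mechanisms to be reported routinely as well. Read together, these could bring a late unrelated death into the AE data. They would then conflict with 10.6132, so a site cannot tell which governs.

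*The deaths are not hidden.* They are in Event Monitoring and in PFS, which runs from registration in both arms. The DSMB reviews safety data at least twice a year. Deaths judged at least possibly related are due under 10.6132 with no end date.

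*The 30-day rule is the same in both arms from the last dose.* The inequality appears only on a clock from Day 1, though a between-arm comparison over a common period needs that clock.

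Some stronger inferences are tempting but not supported. A reader might infer that an unrelated grade 4 event on Day 60 counts in 16.34 while the same event ending in death does not; case 2 shows that the patient still counts. A reader might compare Days 52 and 38 with the 12 weeks in 16.52, but "These toxicities, if they occur, do so within 12 weeks for both Arms A and B" refers to the grade 3 and 4 events and reversible neutropenia cited there, not to deaths from any cause. A reader might conclude that the shorter Arm B window biases the comparison, or that the 16.52 safeguard cannot work. The 14 days are worth under 0.1 expected deaths, and the review still covers submitted grade 4 events and deaths inside the window.

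**Conclusion.** The gap is real but narrow. A death beyond the 30 days that the site judges unrelated need not enter the AE data as grade 5 with a term and attribution. The 16.52 review therefore cannot be relied on to see it, and if no grade 3 or 4 AE came before, it is missing from 16.34.

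Days 52 and 38 hold only if the clock starts at the last dose. The size, about 0.3 to 1.0 all-cause deaths per 58 patients in six months, assumes the survival figures above and a constant hazard. The lower end fits better, because the 90% figure includes patients meeting GELF criteria, who are ineligible here under 3.17. The point is minor: the gain is to the safety check and to clear reporting, not to any test result.

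**What to change.** - Amend 10.6131 and 10.6132 so that every death from Day 1 through the month-6 visit is submitted as a Grade 5 AE with CTCAE term and attribution, whatever the attribution and on the same clock in both arms. Keep the condition of at least possible relation only after month 6.
- State in 16.34 and 16.52 that these deaths are included, and give the 16.34 time window.
- Define procedure in 10.613 or remove it, and reconcile the section with the manufacturer-notification rule in 10.4. Also reconcile Section 18, footnote 3, which limits AE forms and expedited reports to Cycles 1 and 2, with 10.6132 and 10.52, which set no end date for related deaths.

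The cost is a wording change and at most a few extra AE forms, for deaths that Event Monitoring already records. It affects data collection only.
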